#### Sample size

The target sample size of 328 participants is based on data taken from the Phase II study (GEM2), published cohort data [1] and an audit of Edinburgh and Imperial of women undergoing usual care (2012; focusing on those participants with serum hCG >1000 IU/L). The cohort and audit data suggest a 30% rate of surgical intervention in the MTX group, with 15% expected in the MTX and gefitinib group (actual figure from the phase II study was 14% but this has been conservatively rounded up). To detect this absolute difference in proportions of 15% with 90% power and an alpha error rate of 5%, a total of 322 participants would need to be randomised (161 per group). Assuming and adjusting for a 2% loss to follow-up rate, 328 participants need to be recruited.

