#### Handling missing data

In the first instance, analysis will be completed on received data only with every effort made to follow-up participants even after protocol violation to minimise any potential for bias. To examine the possible impact of missing data on the results, and to make sure we are complying with the ITT principle, sensitivity analyses will be performed on the primary outcome measure (surgical intervention) [7]. See section 9.10 for further details.

Data manipulations

See Appendix D.

Analysis methods – primary outcome

A template for reporting the primary outcome is given in section 8.1 of the supplementary analysis report. The primary outcome will be summarised using frequencies and percentages. A mixed effects log-binomial model will be used to generate an adjusted risk ratios (RR) (and 95% CIs). Adjusted risk differences (RD) (and 95% CIs) will also be presented (using an identity link function). Statistical significance of the treatment group parameter will be determined (p-value generated) through examination of the associated chi-squared statistic (this will be obtained from the model which produces the RR). See section 9.1 for covariate adjustment and model convergence.

Analysis methods – secondary outcomes

A template for reporting the secondary outcomes is given in section 8.2 of the supplementary analysis report. See section 9.1 for covariate adjustment and model convergence.

Time to hCG resolution will be considered in a competing risk framework [8]. This is to account for participants who have surgical intervention for their EP, which interferes with the natural path of hCG levels and hence hCG resolution (≤15 IU/L). A cumulative incidence function will be used to estimate the probability of occurrence (hCG resolution) over time. This method is favoured over Kaplan-Meier methods which may overestimate this probability. A Fine-Gray model will be used to estimate subdistribution adjusted hazard ratios (and 95% CIs) directly from the cumulative incidence function. In addition, a further Cox Proportional Hazard model will be fitted and applied to the cause-specific (non-surgical resolution) hazard function and used to generate

adjusted hazard ratios (and 95% CIs) (effectively censoring surgical events at the point of surgery) [9].

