A sensitivity analysis which excludes any women who are found to violate the inclusion/criteria. An analysis to assess the effect of missing responses for the primary outcome only. Unadjusted models will be utilised. This analysis will explore the possibility that missing responses are 'missing not at random' (MNAR) using a tipping point approach. In this analysis, for women with missing outcome data, events will be added sequentially in each of the groups in turn to determine the point where the general conclusion changes (for example from positive to inconclusive in terms of the CI). An assessment can then be made about whether the event rate in the missing responses between groups is likely to be plausible when compared with the event rate in the non-missing data. Two scenarios will be considered as follows:

Scenario A: In the MTX and placebo group, assume all missing responses are non-events (i.e. surgical intervention is no). For missing responses in the MTX and gefitinib group, we will first replace X missing responses with events (i.e. X additional cases of surgical intervention) where X is the number of events such that the event rate in the missing responses is equal to the event rate in the non-missing responses in the MTX and gefitinib group (for example if the event rate in the non-missing data in the MTX and gefitinib group is 30% and we have 10 missing responses we will add  $0.3*10 \sim 3$  events [number of events rounded to the closest integer >0]). This will be regarded as the base case. All other missing responses in the MTX and gefitinib group will be considered as non-events. An unadjusted model will be fitted. Event rates will be compared between groups. The CI from the treatment estimate (from the RR of the log-binomial model) will be examined and stored. Following the base case, an additional event will be added to the MTX and gefitinib group and the above procedure repeated (unadjusted model fitted and the RR and CI examined). This process will end when the number of events added to the MTX and gefitinib group are equal to the original number of missing responses in this group. The tipping point for the MTX and gefitinib group will occur when enough events have been added such that the upper/lower limit of the CI from the corresponding model differs from that of the primary ITT finding (in regards to whether the CI crosses the null value of one).

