Scenario B: In the MTX and gefitinib group, assume all missing responses are non-events (i.e. surgical intervention is no). For missing responses in the MTX and placebo group, we will first replace X missing responses with events (i.e. X additional cases of surgical intervention) where X is the number of events such that the event rate in the missing responses is equal to the event rate in the non-missing responses in the MTX and placebo group (for example if the event rate in the non-missing data in the MTX and placebo group is 30% and we have 10 missing responses we will add 0.3\*10 ~ 3 events [number of events rounded to the closest integer >0]). This will be regarded as the base case. All other missing responses in the MTX and placebo group will be considered as non-events. An unadjusted model will be fitted. Event rates will be compared between groups. The CI from the treatment estimate (from the RR of the log-binomial model) will be examined and stored. Following the base case, an additional event will be added to the MTX and placebo group and the above procedure repeated (unadjusted model fitted and the RR and

CI examined). This process will end when the number of events added to the MTX and placebo group are equal to the original number of missing responses in this group. The tipping point for the MTX and placebo group will occur when enough events have been added such that the upper/lower limit of the CI from the corresponding model differs from that of the primary ITT finding (in regards to whether the CI crosses the null value of one).

For both scenario A and scenario B, results will be presented visually. The event rate (surgical intervention rate) in the missing data in the MTX and gefitinib group (scenario A) or MTX and placebo group (scenario B) will be plotted on the x-axis. The RR (MTX and gefitinib vs. MTX and placebo) from the model will be on the plotted on the y-axis. The corresponding CI will be included around each RR. If the CI in the ITT analysis contains one, then the point where the upper CI falls below or above one will be highlighted (tipping point) on the plot. If the CI in the ITT analysis does not contain one (i.e. one treatment is superior to the other), then the point where the CI crosses one will be highlighted (tipping point). The base case will also be highlighted on each plot.

Sensitivity analyses for the secondary outcomes only will consist of:

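### The tipping-point analysis judges unadjusted intervals against the adjusted ITT interval, and its base case is not a neutral starting point, so a borderline result can tip before any event is added

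*SAP*

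**What the plan says.** **Primary analysis.** SAP section 9.5: "A mixed effects log-binomial model will be used to generate an adjusted risk ratios (RR) (and 95% CIs". Section 9.1 lists the adjustment: hCG category, BMI category and ectopic size as fixed effects, with centre as a random intercept. Section 9.3 restricts this analysis to received data.

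**Tipping-point analysis (section 9.10).** "Unadjusted models will be utilised". Scenario A begins: "In the MTX and placebo group, assume all missing responses are non-events". The missing gefitinib women start with the number of events that matches the observed gefitinib rate, rounded to an integer above zero. This is called the base case, and events are added one at a time from there. Scenario B is the mirror image, with the missing gefitinib women fixed as non-events.

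**Tip rule.** In both scenarios the tip is the point at which "the upper/lower limit of the CI from the corresponding model differs from that of the primary ITT finding", in terms of whether the interval crosses one. For the plots, when the ITT interval contains one, "the point where the upper CI falls below or above one will be highlighted".

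**Role.** The amendment table (SAP Table 1) records that the imputation-based sensitivity analysis was replaced by this one. It is now the only missing-data sensitivity analysis for the primary outcome.

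**The concern.** A tipping-point analysis should show how far the missing outcomes must depart from a neutral assumption before the conclusion changes. Two features of section 9.10 blur that reading.

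1. **Model mismatch.** The reference is adjusted and the intervals compared with it are not. A difference between them can come from the covariates and have nothing to do with missing data.
2. **Base case.** A reader will take the base case, highlighted on each plot, as neutral. It is neutral in the varied arm only, apart from rounding. The other arm's missing women are held at 0% events, whatever that arm's observed rate. The x-axis shows only the varied arm's rate, so a tip at the base case looks like fragility at the observed rate when the fixed 0% in the other arm caused it.

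A third point concerns wording. The plot rule names only the upper limit. If the ITT interval contains one, its upper limit is already above one, and a shift to harm happens when the lower limit passes one.

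At stake is how the trial's one check on missing primary outcomes is read.

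**Working it through.** **Inputs from the SAP (section 4.7).** "30% rate of surgical intervention in the MTX group", "with 15% expected in the MTX and gefitinib group", "with 90% power and an alpha error rate of 5". Loss to follow-up is 2%.

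**Reproducing the sample size.** Pooled-variance formula, two-sided, no continuity correction, mean rate 0.225:

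n per arm = [1.960·√(2·0.225·0.775) + 1.282·√(0.30·0.70 + 0.15·0.85)]² / 0.15² = 160.8, so 161 per arm and 322 in total, as stated. 322/0.98 = 328.6, against the stated 328. That is about 164 per arm, with about 3 missing per arm.

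**Interval used below.** RR = (a/n₁)/(b/n₀); SE(log RR) = √(1/a − 1/n₁ + 1/b − 1/n₀); 95% CI = exp(log RR ± 1.96·SE). Gefitinib is listed first.

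**Base case, 3 missing per arm.**

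| Data | Table | RR (95% CI) |
|---|---|---|
| Observed | 32/161 v 48/161 | 0.667 (0.451 to 0.985) |
| Scenario A base case | 33/164 v 48/164 | 0.688 (0.467 to 1.012) |
| Both arms at observed rates | 33/164 v 49/164 | 0.673 (0.458 to 0.989) |
| Observed | 33/161 v 48/161 | 0.688 (0.468 to 1.011) |
| Scenario B base case | 33/164 v 49/164 | 0.673 (0.458 to 0.989) |
| Both arms at observed rates | 34/164 v 49/164 | 0.694 (0.474 to 1.015) |

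Imputed events are 3 × 32/161 = 0.60, 3 × 33/161 = 0.61 and 3 × 48/161 = 0.89, each rounded to 1. Scenario A turns a positive result inconclusive, and Scenario B turns an inconclusive one positive. With both arms at their observed rates neither conclusion changes.

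**At the design rates.** Observed 24/161 v 48/161 gives 0.500 (0.322 to 0.775). Scenario A's base case, 25/164 v 48/164, gives 0.521 (0.338 to 0.802). With all three missing gefitinib women as events, 27/164 v 48/164 gives 0.563 (0.370 to 0.855). There is no tip at any step.

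**How often the base case flips.** 20,000 simulated trials per setting, 164 per arm, reference = unadjusted observed-data CI, so that only the base-case effect is counted. Losses of 8 and 16 per arm are assumptions.

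| True rates | Missing per arm | Scenario A | Scenario B | Both at observed rates |
|---|---|---|---|---|
| 15% v 30% | 3 | 3.1% | 2.1% | 0.4% |
| 15% v 30% | 8 | 3.8% | 4.0% | 1.6% |
| 15% v 30% | 16 | 11.0% | 7.8% | 2.1% |
| 20% v 30% | 3 | 6.1% | 4.5% | 0.9% |
| 20% v 30% | 8 | 9.6% | 9.5% | 2.0% |
| 20% v 30% | 16 | 18.5% | 20.6% | 4.2% |
| 30% v 30% | 3 | 1.4% | 1.4% | 0.3% |

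The remainder in the last column comes from integer rounding and the larger denominator.

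**Model mismatch with no missing data.** The adjusted and unadjusted intervals were compared on whether they cross one. The SAP gives no covariate effects, so these are assumed.

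- hCG relative risks 0.6/1.0/1.6 and size relative risks 0.85/1.15, 1,500 runs: disagreement in 0.7% (15% v 30%), 2.2% (20% v 30%) and 0.8% (30% v 30%).
- Log-risk slope 0.35 to 0.5 per SD of log hCG, RR 0.50 to 0.65, N = 322, 400 trials per setting: 4.8%, 6.8% and 11.8%.
- The same slopes, 600 trials: about 3 to 4% at 15% v 30%, and 7 to 7.5% at RR 0.65.

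The first two sets used modified Poisson regression with robust errors and no centre term, in place of the mixed log-binomial model.

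**Plot rule.** Assume 10 missing per arm and observed 45/154 v 31/154: RR 1.452 (0.974 to 2.164). Scenario A's base case adds 10 × 45/154 = 2.9, or 3 events: 48/164 v 31/164, 1.548 (1.042 to 2.302). The conclusion has moved to harm through the lower limit. The upper limit was above one throughout, so the plot sentence would mark nothing.

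**The case against.** The analysis is declared as an exploration of outcomes missing not at random, so a non-neutral start is arguably its purpose. The unadjusted models are openly pre-specified. The base case is highlighted, the plausibility of the missing-data event rates is to be assessed, and no rule lets a tip overturn the ITT conclusion. Varying one arm at a time is an accepted layout. All of this stands, and it keeps the point small. It does not supply a like-for-like reference or a fit with both arms at their observed rates, and without those the plausibility judgement lacks its anchor.

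Some stronger readings are not supported:

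- **Scenario B is defective because adding placebo events cannot tip a result that favours gefitinib.** The two scenarios test opposite directions and were fixed before the direction was known. Scenario B is informative when the ITT result is inconclusive, as 33/161 v 48/161 shows, or favours placebo.
- **The other arm is given no events.** Only its missing women are set to non-events; its observed events stay.
- **The integer-above-zero rounding distorts the analysis.** With 3 missing and a 15% rate, 0.45 becomes 1 event (33%), but the only alternative is 0%. The difference is one event in 164.
- **The plan ignores the lower limit.** The tip definition in both scenarios names both limits. Only the plot sentence is narrower, so this is a matter of aligning two statements.

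**Conclusion.** The concern holds in a limited form. As written, the rule can show a tip that comes from the change of model or from the fixed 0% in the other arm's missing women, before any event is added beyond the base case.

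A reader might infer that the analysis tips with no departure from missing at random. That is exact only for the model-mismatch route. In the base-case route the 0% is itself a departure, but the label hides it. A reader might also infer that robust results will be called fragile. The figures do not show that: the flips are in results whose interval already lies close to one, and the design-rate example does not tip.

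At the planned loss, base-case flips occur in about 1 to 6% of simulated trials across the rates tried, rising to about 4 to 21% with 8 to 16 missing per arm when the true rates differ. The model-mismatch figure, roughly 1 to 12%, rests wholly on assumed covariate effects and should be read as a range. Severity is minor.

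**What to change.** Amend SAP section 9.10 as follows:

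1. Judge every tipping-point fit against the unadjusted complete-case interval, or use the adjusted primary model throughout.
2. Fit, and mark as the base case, the cell in which each arm's missing women have that arm's own observed event rate, rounded to the nearest integer with zero allowed.
3. Vary both arms over a grid from no missing women to all missing women as events. Scenario A then lies along the edge with no events among the missing placebo women, and Scenario B along the edge with none among the missing gefitinib women.
4. Align the plot sentence with the tip definition, so that a change through either limit is marked, including a lower limit that passes above one.

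Cost: a short wording change, a two-way display in place of two single plots, and a loop over a few more models. There are 4 × 4 = 16 cells for 3 missing per arm, and 11 × 11 = 121 for 10. The primary analysis, sample size and data collection are unaffected.

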Appendix A: Deviations from SAP

This report below follows the statistical analysis plan dated <insert effective date of latest SAP> apart from following:

Section of report not following SAP	Reason
<insert section=""></insert>	<insert, analyses="" by="" e.g.="" exploratory="" request="" tmg=""></insert,>

#### **Appendix C: Schedule of assessments**

	Day of Treatment	Standard Clinical Care Visits	Day 14 – 21^ (during scheduled clinical care visits)	
Consent	$\checkmark$	√*	√*	√ *
Clinical Assessment	✓	✓	✓	
Serum hCG (within 1 day)	v	*	V	
FBC, U&Es, LFTs (within 3 days of treatment)**	✓		✓	
Adverse Events		√ ***	$\checkmark$	
Compliance		$\checkmark$		
Telephone consultation				✓

\*Ongoing consent will be confirmed at each visit

\*\*Until back to within normal ranges and stop date documented where applicable

\*\*\*If this clinical appointment falls when research staff are not available, the local research team will contact the participant at the earliest possible date to ascertain any AEs.

^ Sites will define day of MTX treatment as either day 0 or day 1 depending on local policies.

#### **Appendix D: Data Manipulations**

The Trial Statistician will derive the following measures as follows:

#### Outcome measures

# Surgical intervention for the treatment of EP (salpingectomy or salpingostomy by laparoscopy or laparotomy)

Reported on the surgical intervention form. If a surgery form has been completed and either 'salpingectomy' or 'salpingostomy/salpingotomy' are yes then this will meet the primary outcome definition (i.e. surgical intervention=yes). On the post-treatment visit form, if a woman has been followed up until her hCG levels are  $\leq 15$  IU/L and 'surgical intervention required' is no (or surgical intervention is yes but neither a salpingectomy or salpingostomy/salpingostomy have been performed) then this will not meet the primary outcome (i.e. surgical intervention=no). On the post-treatment visit form, if a woman has not been followed up until her hCG levels are  $\leq 15$  IU/L, but we have confirmation from site that no surgery was performed then this will not meet the primary outcome (i.e. surgical intervention=no).

#### Use of additional MTX

Use of additional MTX is reported on the post-treatment visit form. If 'further dose of MTX required today or since last visit' is yes at any visit (up to resolution) then this will meet the outcome definition (i.e. use of additional MTX=yes). If 'further dose of MTX required today or since last visit' is no at all visits (up to resolution) then this will not meet the outcome definition (i.e. use of additional MTX=no). If a woman does not have a post-treatment visit as a result of immediate surgery following randomisation we will assume additional MTX=no. All other responses will be considered missing.

#### Time to hCG resolution (days) from randomisation until hCG levels ≤15 IU/L

If a woman is followed up to a hCG  $\leq$ 15 IU/L (and did not receive surgery or hCG was  $\leq$ 15 IU/L prior to receiving surgery) the pregnancy will be regarded as having resolved. Date of randomisation will be regarded as time 0 and time to hCG resolution will be derived as follows:

Time to hCG resolution (days) = (Date of hCG measurement\*-Date of randomisation)

\*Where date of hCG measurement is the earliest date post-randomisation where hCG level is  $\leq$ 15 IU/L.

If a woman has not been followed up to a hCG ≤15 IU/L (and did not receive surgery) the pregnancy will be regarded as unresolved and the woman will be censored at the point of her most recent follow-up visit where a hCG measurement was reported. Time to follow-up for censoring will be derived as follows:

Time to follow-up (days) = (Date of hCG measurement\*\*-Date of randomisation)

\*\*Where date of hCG measurement is the most recent date post-randomisation where hCG level is measured.

If a woman received surgery (salpingectomy or salpingostomy/salpingotomy) prior to hCG resolution ( $\leq$ 15 IU/L), the pregnancy will be regarded as unresolved and the woman will be censored at the point of surgery (as a competing risk). Time to surgery for censoring will be derived as follows:

Time to surgery (days) = (Date of surgery-Date of randomisation)

If time to hCG resolution, time to follow-up or time to surgery are equal to zero, a continuity correction of 0.01 days will be added (Stata unable to process zero time).

Time to hCG resolution (days) from randomisation until hCG levels ≤30 IU/L (Sensitivity analysis)

As per 'time to hCG resolution (days) from randomisation until hCG levels  $\leq$ 15 IU/L' but hCG threshold changed to  $\leq$ 30 IU/L.

Number of hospital visits associated with treatment until resolution or scheduled/emergency surgery

Number of hospital visits associated with treatment are reported on the post-treatment visit form.

Remove any post-treatment visits which occur post resolution (where resolution occurs when a woman receives surgery (salpingectomy or salpingostomy/salpingostomy) or her hCG levels fall ≤15 IU/L).

Firstly, we look at the number of extra visits related to the EP:

If 'Have you had any extra visits to hospital related to this EP'=no then number of additional visits=0.

If 'Have you had any extra visits to hospital related to this EP'=yes then number of additional visits should be provided.

If a woman does not have a post-treatment visit as a result of immediate surgery following randomisation we will assume number of extra visits=0.

Where a woman has X post-treatment visits, sum the total number of extra visits (A) as follows:

A=(Number of extra visits at visit 1 + Number of extra visits at visit 2 + ... + Number of extra visits at visit X)

Secondly, we look at the number of hospital attendances:

Remove any post-treatment visits where a woman did not have a hospital visit (hCG measurement/USS scan/additional MTX used as a proxy for hospital attendance i.e. if none of these are performed we can assume the visit was conducted remotely). Count the number of post-treatment visits with hospital attendance (X). The number of hospital attendances (B) can be calculated as follows:

If a woman had surgery and this occurred on a different day to a post-treatment visit then

B=X+1

If a woman did not have surgery or surgery occurred on the same day as a post-treatment visit then

B=X

Finally, the total number of hospital visits associated with treatment can then be calculated as follows:

Total number of hospital visits associated with treatment=A+B

Length of follow-up (in days) for the offset term for the Poisson model will be calculated as:

Date of resolution\*-Date of randomisation

\*Date of resolution is date of surgery (salpingectomy or salpingostomy/salpingostomy) or earliest date post-randomisation where hCG level is  $\leq$ 15 IU/L. If a date of resolution is missing (no surgery and not followed up to a hCG  $\leq$ 15 IU/L) and site have confirmed woman's pregnancy has resolved and no surgery performed, date of most recent hCG measurement will be used as date of resolution.

